#### **5 STUDY EVALUATIONS AND MEASUREMENTS**

#### 5.1 Screening/Baseline and Monitoring Evaluations and Measurements

#### 5.1.1 History and Medical Record Review

Review of medical records will be conducted, including review of paper and electronic records of subjects, to confirm ophthalmologic history, inclusion/exclusion criteria, and pertinent past medical history. Those items that will be abstracted from the medical chart (paper and electronic) will include age, gender, race (demographic information), relevant past ophthalmologic and medical history including visual acuity, visual fields, genotype, concomitant medications, laboratory reports, electroretinograms (ERG), fundus photographs, optical coherence tomograms, radiological and scanning results, ultrasound results, pathology reports, and other relevant clinical information. If the subject is entered on study, the medical history will be updated in a longitudinal manner, to determine if any significant events have occurred during the course of follow-up, and to document concomitant medication changes.

#### 5.1.2 Physical Examination

Screening/Baseline and interim physical examinations will include measurements of vital signs as well as general physical examination. The Investigators, or qualified designee, will perform physical examinations and measure body weight and height at the time points specified in the schedule of assessments. In addition, symptom-oriented physical examinations will be performed when clinically indicated. Clinically relevant abnormalities prior to the first dose of investigational product will be recorded as medical history; clinically relevant abnormalities after the first dose of investigational product will be recorded as AEs.

#### 5.1.3 Laboratory Evaluations

Blood sampling will be performed for the following standard clinical laboratory evaluations (see Table 5.1.3.1); repeat analysis and/or additional sampling and testing will be performed when clinically indicated:

- Sequence analysis of the CHM gene by a CLIA-certified laboratory
- Hematology (CBC and differential)
- Chemistry panel to include liver and renal function tests
- Virology testing to include HIV screen

Urine testing will be performed by standard clinical laboratory analyses (see Table 5.1.3.1); repeat analysis and/or additional sampling and testing will be performed when clinically indicated:

• Urinalysis (UA) including pH, color, and microscopic exam

Analysis will be performed for the following research laboratory evaluations (see Table 5.1.3.2):

- AAV Viral Capsid Antibody
- PBMC for ELISpot
- Whole blood and serum for PCR analysis (vector shedding)

• Tears collected for vector shedding by PCR analysis

Category	Tests
CHM gene analysis	Sequence/mutation analysis by CLIA-certified laboratory
Hematology	CBC and differential
Chemistry panel	Standard panel per clinical laboratory (including liver and renal function tests)
Virology tests	Screening tests for HIV
Urinalysis	Standard urinalysis per clinical laboratory

#### 5.1.3.1 Table: Summary of Clinical Laboratory Tests

5.1.3.2 Table: Summary of Research Laboratory Tests

Category	Tests
AAV Viral Capsid Antibody	Measurement of antibody against AAV viral capsid, serotype 2
PBMC for ELISpot	PBMC evaluation for IFN $\gamma$ to evaluate activation of immune response
Whole blood and serum for vector sequences	Blood specimens are collected, DNA is extracted, and PCR analysis conducted
Tears for vector sequences	Tear specimens are collected, DNA is extracted, and PCR analysis conducted

Each test is conducted according to Sponsor or designee standard operating procedure (SOP).

Ophthalmic tests will be performed for the following standard and research evaluations (see Table 5.1.3.3):

- Ophthalmic examination
- Visual acuity
- Humphrey visual field tests
- Octopus kinetic visual field test (for subjects whose central visual field is >20° in at least 1 of the 24 meridians at the Screening/Baseline visit using Goldmann perimetry III4e isopter)
- Reading speed
- Contrast sensitivity
- Color vision test
- Microperimetry
- Full-field light sensitivity threshold testing
- Fundus photography (including low intensity autofluorescence)
- OCT
- QOL questionnaire

Category	Tests			
Visual Function	Ophthalmic examinations, using standard instruments and methods			
	Visual Acuity (ETDRS)			
	Goldmann Visual Field Test (III4e isopter)			
	Humphrey Visual Field Tests			
	Octopus Kinetic Visual Field Test 			
	Contrast Sensitivity			
	Color vision test			
	Microperimetry			
	Full-field Light Sensitivity Threshold Testing			
Functional Vision	Reading Speed			
Imaging	Fundus Photography			
	Optical Coherence Tomography (OCT), to measure retinal thickness			
Evaluation of activities of daily life	QOL Questionnaire			

#### 5.1.3.3 Table: Summary of Ophthalmic Tests & Evaluations

Each test is conducted according to standard ophthalmology office practice or Sponsor or designee SOP. Octopus kinetic visual field test will only be done to subjects whose central visual field is >20° in at least 1 of the 24 meridians at the Screening/Baseline visit using Goldmann perimetry III4e isopter.

#### **5.2 Efficacy Evaluations**

Evaluations will be made for visual acuity, Goldmann and Humphrey visual field tests, Octopus kinetic visual field test, reading speed, contrast sensitivity, color vision test, microperimetry, full-field light sensitivity threshold testing, fundus photography (including low intensity autofluorescence), optical coherence tomography (OCT), and QOL questionnaire. Each of these tests is either a standard clinical test done according to standard clinical practice or performed by the investigative team according to Sponsor SOP.

Visual Acuity: Visual acuity measures will document any change in central vision, the ability to resolve standard optotype images presented as optotypes/letters corresponding to different visual angles, *i.e.*, image size. This testing will use ETDRS charts. The level of central visual resolution is converted to a visual minimal angle of resolution score (LogMAR) for comparison purposes.

Visual Field Tests: Visual field parameters will evaluate alterations in function of different regions of the retina; kinetic fields will be measured with Goldmann (III4e isopter), and Humphrey static fields with computerized testing, including foveal and macular thresholds, and a central field. In addition, Octopus kinetic perimetry will be done to subjects whose central

visual field is  $>20^{\circ}$  in at least 1 of the 24 meridians at Screening/Baseline visit using Goldmann perimetry III4e isopter.

Reading speed: The reading speed test will require subjects to read designated word charts with black letters on a white background aloud and subsequently, the critical print size and optimal reading speed will be calculated.

Contrast Sensitivity: Contrast sensitivity will measure the subject's ability to discern targets presented at varying levels of contrast.

Color Vision Test: Color vision testing will be conducted if the subjects are able to perceive the test objects.

Microperimetry: Microperimetry will be conducted in the dark-adapted state to evaluate maximal retinal sensitivity. Microperimetry measurements of the injected eyes will also be compared to the control (uninjected) eyes. Microperimetry will measure minimal detectable stimulus, mean sensitivity, and visual field size.

Full-field Light Sensitivity Threshold Testing: Full-field light sensitivity threshold (FST) testing measures the light sensitivity of the entire visual field by recording the luminance at which a subject reports seeing the dimmest flash. The test is carried out on subjects with dilated eyes in a dark-adapted state; subjects are seated in front of a Ganzfeld dome in which the light flashes are generated. The light sensitivity of each eye is measured separately by removing patches from one eye (and then the other). A sound is generated at the time of the light flash and the subject presses one button when they see a flash or a second button if they do not see a flash. Flashes of varying luminance (in a range spanning ~80 dB) are presented in a randomized order, except that the series starts with dim flashes. From this data, an algorithm calculates the minimum luminance (for each eye) at which the subject preceives light.

Fundus Photography: Fundoscopy will be performed with indirect ophthalmoscopic exam and fundus biomicroscopy. Photographs will be taken with a fundus camera following standard clinical methods.

Optical coherence tomography (OCT): OCT captures micrometer-resolution, three-dimensional images from within optical scattering media (*e.g.*, retinal tissue). The Heidelberg Spectralis OCT machine will be used. Optical coherence tomography is an interferometric technique, typically employing near-infrared light. The use of relatively long wavelength light allows it to penetrate into the scattering medium, providing important images, including the thickness of the retina.

Quality of Life questionnaire: The Investigators will use a QOL questionnaire relevant to the subject population.

#### **5.3 Safety Evaluations**

Safety will be monitored and data captured by description of adverse events and pregnancy outcomes in female partners of subjects post vector administration. Adverse events will be reported to the regulatory agencies that oversee gene therapy trials, including the Sponsor, local

IRB and IBC, FDA, NIH OBA, and the independent DSMB. The reporting details are more thoroughly described in Section 8.

## 6 STATISTICAL CONSIDERATIONS

Safety analyses will be performed for all participants that receive AAV2-hCHM. Summary statistics will be provided to evaluate efficacy endpoints by dose group for all evaluable subjects. Each subject's *CHM* gene sequence information will be obtained for information only. Because of the small sample size, it is not anticipated that any statistically significant correlation will be possible between a particular mutation in the *CHM* gene and safety and efficacy outcomes.

Efficacy data will be collected; however, because of the number of subjects and the size of the dosage groups it is likely that the study lacks sufficient power to reach statistical significance. If the study results in favorable safety and tolerability profile of AAV2-hCHM, as well as an indication of efficacy, follow-on studies will be proposed to more completely evaluate statistical significance and clinical applicability of this gene therapy approach.

## 7 INVESTIGATIONAL PRODUCT (INTERVENTION)

The investigational product is AAV2-hCHM is an AAV serotype 2 vector containing singlestranded DNA encoding the human *CHM* gene driven by the chicken  $\beta$  actin (C $\beta$ A) promoter/CMV enhancer upstream of C $\beta$ A exon 1 and intron.

The vector production facility and methods have been characterized by the Manufacturer, CCMT CVC (Wright, 2008; Wright *et al.*, 2010; Wright & Zelenaia, 2011).

The gene therapy material to be used in this clinical study has been manufactured under current Good Manufacturing Practices (cGMP).

The final formulation of the

#### 7.1 Packaging

AAV2-hCHM is derived from a virus and should be considered and handled as an infectious agent. AAV2-hCHM is supplied as a frozen liquid at a volume of 1 mL in a 1.5 mL polypropylene sterile cryogenic screw cap vial. AAV2-hCHM is to be stored frozen at less than -60°C. Just prior to use, the frozen product will be thawed at room temperature. The syringe for AAV2-hCHM transport and administration will be prepared sterilely and filled in a bio-safety cabinet. After filling, the syringe is stored at room temperature. Within the operating room, the syringe is coupled to the surgical device. The product is to be administered within six hours of thawing to assure maximum potency. Preparation materials will be maintained by the investigational pharmacy for a period of two months; at this time, they will be destroyed or shipped back to the Sponsor, per instructions.

A qualified pharmacist with specific training on this protocol will be responsible for vector receipt from the Sponsor, storage, documentation of traceability of investigational product at the investigational site, and preparation (dilution) on the day of surgery. Prior to dispensing of the investigational product from the investigational pharmacy for administration to a study subject, a Pharmacy Order Form shall be completed and signed by a Principal Investigator or qualified Sub-Investigator. This form is to be completed on a subject-by-subject basis; the Investigators should complete and initial the date and time section. Upon receiving the order form, the investigational pharmacy will prepare the investigational product as follows:

Universal precautions and appropriate personal protective equipment will be used by investigational pharmacy personnel performing the dilution. The frozen AAV2-hCHM and diluent vials shall be thawed at room temperature and gently mixed. Appropriate volumes of the AAV2-hCHM and diluent products, both provided by the Sponsor, will then be combined using aseptic techniques in a biosafety cabinet. The Sponsor's instructions for this procedure, including the specific volumes of AAV2-hCHM and diluent to combine, will accompany each individual lot of material delivered to the investigational pharmacy.

#### 7.2 Labeling

The product label indicates: Investigational product name (AAV2-hCHM); manufacturer (CCMT CVC, Children's Hospital of Philadelphia PA, USA); specific lot number; date of manufacture; vial number; storage instructions (< 60°C); and investigational product warning (Caution: New Drug – Limited by Federal Law to Investigational Use).

## 7.4 Stopping Rules

The toxicity criteria are based on the WHO toxicity scale, with added assessments pertaining to ocular AEs (located in the Manual of Procedures). Dose-limiting toxicity (DLT) will be defined as any irreversible Grade 3 or higher toxicity, or any reversible Grade 4 toxicity, that is possibly or probably related to AAV2-hCHM. Irreversible toxicities are defined as those that persist at the same (or higher) grade for more than seven days; reversible toxicities are those resolving in seven or fewer days.

If DLT is experienced, further subject enrollment will be delayed pending consultation with the DSMB. If a subject experiences any DLT, the DSMB will assist in determining whether additional subjects should be enrolled at the same dose level, or at a lower dose level. If two subjects of a dose group develop limiting toxicity, possibly or probably attributable to the vector, the maximum tolerated dose (MTD) will have been reached. In the event this occurs in Dose Group 2, additional subjects may be enrolled to the group just below the MTD, *i.e.* Dose Group 1.

If a single occurrence of Grade 4 toxicity, excluding toxicities covered under the category "General", or death of a subject occurs and is deemed possibly or probably related to the AAV2-hCHM, the Sponsor will halt enrollment and notify the DSMB and FDA. Further enrollment and/or vector administrations will be conducted only after FDA and the Sponsor confer to determine that the IND is not on clinical hold, and the DSMB agrees to continue enrollment. Study visits for subjects that have already received AAV2-hCHM will continue per protocol.

The Sponsor or designee will report all SAEs and AEs to the DSMB, FDA, NIH OBA, and to Principal Investigators (who will in turn notify the IRBs/Institutional Ethics Committees (IECs) of record) within the required reporting timeframes. In addition to the stopping rules outlined above and based on the toxicity criteria table (located in the Manual of Procedures), the Sponsor will respond to recommendations of the DSMB.

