#### 8.2 Adverse Event Reporting

All events described by the subject will be reported as AEs, regardless of toxicity grade in.

Protocol-defined safety laboratory test results will be collected prospectively and analyzed separately as part of the study. Additional laboratory test results at other time points may be available to the Investigators as part of standard clinical practice. Throughout the active phase of the study, laboratory-related abnormalities should be recorded as AEs only if considered clinically significant, outside the range of expected values given the subject's baseline assessments and clinical course, and not known to be part of another AE diagnosis. As per regulatory guidelines, pre-existing conditions, including abnormal lab values manifest at baseline testing, will only be reported as adverse events if the condition worsens in severity and/or frequency.

The Investigators will follow an AE until the event is either resolved or assessed as stable.

The Investigators are responsible for notifying the Sponsor representative or designee and the IRB of all AEs and other unanticipated problems related to research. Unanticipated problems are other types of incidents, experiences, and outcomes that occur during the conduct of human subject research that are not considered adverse events. For example, some unanticipated problems involve social or economic harm instead of the physical or psychological harm associated with adverse events. In other cases, unanticipated problems place subjects or others at increased *risk* of harm, but no harm occurs.

The Sponsor or designee will notify the appropriate federal regulatory authorities (FDA, NIH OBA, DSMB). Events that do not require expedited reporting will be summarized at the time of continuing review / annual report.

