#### 8.5 Grading of Adverse Events

Adverse events will be graded for intensity as mild, moderate, severe, life-threatening, or resulting in death as defined below. If applicable, the toxicity grade found in the Manual of Procedures should also be noted.

Grade	Description
Mild	Symptom barely noticeable to the subject and does not influence his/her performance or functioning.
Moderate	Symptom of a sufficient severity to make the subject uncomfortable or hinder the performance of daily activities; treatment of symptom may be needed.
Severe	Symptom causes severe discomfort; treatment for symptom may be given and/or subject may be hospitalized.
Life- threatening	Occurrence of the event places the subject at immediate risk of death.
Death	Occurrence of the event results in the death of the subject.

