For SAEs, the initial notification should include all available information requested on the SAE Form; the initial notification must be followed by written documentation, which includes all information including causality assessment from the Principle Investigator. The SAE Form will collect data surrounding the event, *e.g.*, the nature of the symptom(s), time of onset in relation to initiation of investigational product, duration, severity, and whether or not treatment was administered for the symptoms experienced. The Investigator's assessment of the probable cause of the event will also be included. A physician will examine subjects who experience an SAE or a medical emergency situation as soon as possible. The physician in attendance will do whatever is medically necessary for the safety and well-being of the subject. The subject will remain under observation as long as medically indicated in the opinion of the Investigator. Appropriate lab studies will be conducted until all parameters return to normal or are otherwise explained. The SAE will be followed until resolved or until medically stabilized. In a medical emergency requiring immediate attention, study site staff will provide appropriate medical care, according to current standards of care. The Investigator or his/her designee should contact the Sponsor or designee Medical Monitor. The Sponsor or designee will notify the appropriate federal regulatory authorities.

If an SAE has not resolved at the time of the initial report, a follow-up report including all relevant new or reassessed information (*e.g.*, concomitant medication, medical history) should be submitted to the Sponsor or designee. All SAEs should be followed until either resolved or stable. The Medical Monitor and the independent DSMB will review all AEs.

Investigator safety reports must be prepared for suspected unexpected serious adverse reactions (SUSARs) according to local regulatory requirements and Sponsor policy, and forwarded to Investigators as necessary. An Investigator who receives an investigator safety report describing an SAE or who receives other specific safety information (e.g., summary or listing of SAEs) from the Sponsor will review and then file it along with the Investigator's Brochure and will notify the IRB/IEC if appropriate according to local regulatory reporting requirements.

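### Protocol 7.4: read literally, a related Grade 4 toxicity that improves to Grade 2 or lower within seven days but has not cleared by day 7 is not a DLT, while one that clears fully is (minor)

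*Protocol*

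**What the plan says.** Protocol 7.4 (Stopping Rules) gives two routes to a DLT, both requiring at least a possible relationship to the vector: an irreversible toxicity of Grade 3 or above, or a reversible toxicity of Grade 4. The two adjectives are then defined:

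- The first is defined by how long the grade is held: "Irreversible toxicities are defined as those that persist at the same (or higher) grade for more than seven days"
- The second is defined by time to resolution: "reversible toxicities are those resolving in seven or fewer days"

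The grading scale is the WHO scale "with added assessments pertaining to ocular AEs (located in the Manual of Procedures"). Protocol 8.5 likewise refers the reader to that manual: where applicable, "the toxicity grade found in the Manual of Procedures should also be noted". The manual is not among the documents.

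Three consequences follow in 7.4:

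- Any DLT delays further enrolment until the DSMB has been consulted.
- "If two subjects of a dose group develop limiting toxicity, possibly or probably attributable to the vector", the maximum tolerated dose (MTD) has been reached.
- Separately, and with no reference to duration, "If a single occurrence of Grade 4 toxicity, excluding toxicities covered under the category" General, occurs and is judged at least possibly related, the sponsor stops enrolment and informs the DSMB and FDA.

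The Synopsis (Statistical and Analytic Plan) names limiting toxicity as the primary statistical endpoint. The SAP has no DLT definition of its own, so 7.4 is the only one.

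**The concern.** The two definitions look like a complementary pair, but they measure different things. Irreversible asks whether the toxicity held its grade beyond seven days. Reversible asks whether it was gone by then. An event can do neither: it leaves its grade early and lingers at a lower one.

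For Grade 4 toxicity the result is perverse. The subject who recovers completely within the week counts as a DLT, and the subject who recovers more slowly does not. That cannot be the intention.

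At stake is the formal DLT count, and through it the two-subject MTD rule. With planned groups of 5 and 10, one subject classified differently can decide whether that rule is met.

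**Working it through.** There is no figure in the plan to reproduce. The check applies the wording of 7.4 to specific courses.

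**Inputs (Protocol 7.4).** For one related event, let *p* be the number of consecutive days at Grade 3 or higher, and *T* the number of days from onset to full resolution.

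- Irreversible, Grade 3 or above: *p* > 7.
- Reversible Grade 4, with resolving taken literally: peak grade 4 and *T* ≤ 7.
- DLT: either condition.
- Gap: peak grade 4, *p* ≤ 7 and *T* > 7.

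**Results.** The last column applies the definition proposed under the fix.

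| Course | *p* | *T* | 7.4 read literally | Proposed definition |
|---|---|---|---|---|
| Grade 4 for 5 days, then clear | 5 | 5 | DLT (reversible) | DLT |
| Grade 4 for 5 days, then Grade 2 to day 21 | 5 | 21 | **not a DLT** | DLT |
| Grade 4 for 3 days, Grade 3 for 3 days, then Grade 2 to day 21 | 6 | 21 | **not a DLT** | DLT |
| Grade 4 for 5 days, then Grade 1 to day 21 | 5 | 21 | **not a DLT** | DLT |
| Grade 4 for 5 days, then Grade 3 to day 21 | 21 | 21 | DLT (irreversible) | DLT |
| Grade 4 for 10 days, then clear | 10 | 10 | DLT (irreversible) | DLT |
| Grade 3 for 10 days, then clear | 10 | 10 | DLT (irreversible) | DLT |
| Grade 3 for 5 days, then Grade 2 to day 21 | 5 | 21 | not a DLT | not a DLT |

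The gap is confined to Grade 4 events that reach Grade 2 or lower within seven days and then linger. The proposed definition closes it and leaves both Grade 3 rows unchanged.

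**Alternative reading.** If resolving meant dropping below Grade 4, every Grade 4 event would either leave that grade within seven days (reversible) or hold it longer (irreversible). There would then be no gap. Section 7.4 does not say this.

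**Effect on the MTD rule (illustration only).** Two subjects in one dose group each have 3 days at Grade 4. The first then clears: *T* = 3, a DLT. The second stays at Grade 2 until day 30: *p* = 3 and *T* = 30, which falls in the gap.

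- Literal reading: 1 DLT, which is 1/5 = 20% in Dose Group 1 or 1/10 = 10% in Dose Group 2. MTD not reached.
- Alternative reading or proposed definition: 2 DLTs, which is 2/5 = 40% or 2/10 = 20%. MTD reached.

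**The case against.** **The ordinary reading closes the gap.** Reversible and irreversible are used as opposites, so a clinician would probably take reversible to mean no longer at that grade. This is a fair reading and may be the intended one. But 7.4 does not state it, and the protocol elsewhere treats resolution as an end state distinct from stability. Protocol 8.2 says "The Investigators will follow an AE until the event is either resolved or assessed as stable", and 8.8 says "The SAE will be followed until resolved or until medically stabilized". Those sentences set how long events are followed and do not define the term for 7.4, so they do not settle the matter either way. The Manual of Procedures might.

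**Subjects are already protected.** This largely stands. A related Grade 4 event outside General halts enrolment whatever its duration. Restart needs DSMB agreement and confirmation with FDA that there is no clinical hold, which is stricter than the delay a DLT brings. The DSMB also reviews all adverse events (8.8), and dose escalation needs its approval (3.2). A reader might infer that the gap lets dosing continue unchecked after a Grade 4 event, and the documents do not support that. What the halt does not do is make the event a DLT or add it to the two-subject count. For General Grade 4 events, which the halt excludes, the DLT rule is the only formal enrolment delay in 7.4.

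**Two further inferences fail.**

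- A reader might take the same grade to mean the event's peak grade, so that a Grade 4 event settling at Grade 3 is also missed. Nothing exceeds a peak, so that reading leaves the words in brackets, *or higher*, with no work to do. Such an event is best read as already a DLT once it has been at Grade 3 or higher for more than seven days.
- A reader might infer that scheduled visits are too far apart to apply a seven-day cut-off. Grades are not learned only at scheduled visits. Protocol 8.1 has ongoing adverse event inquiry, including by telephone and e-mail. Section 5.1.2 adds symptom-oriented examinations, and 8.3 records onset and end dates.

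**Conclusion.** The definitions in 7.4 are not exhaustive when read literally, and the course they miss is worse than one they catch. That follows from the wording alone and needs no assumption about rates. It does depend on taking resolving to mean fully resolved, and on the Manual of Procedures not saying otherwise.

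The consequence is narrow: the formal DLT count, the two-subject MTD rule, and the enrolment delay for General Grade 4 events. Within a group the swing from one such event is one DLT, which matters to the MTD rule only when exactly one other subject already counts. How often this would happen is unknown, because the documents give no rate for such events. A reader might infer a large gap from the number of conceivable courses that fall in it, but that number depends on the time horizon chosen and says nothing about frequency.

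Severity: minor. It is an ambiguity in a rule that feeds the named primary statistical endpoint, and it is worth one sentence.

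**What to change.** In Protocol 7.4, replace the reversible/irreversible wording with a single definition: a DLT is (a) any toxicity of Grade 4 or higher, whatever its duration, or (b) any Grade 3 toxicity that stays at Grade 3 or higher for more than seven days, in either case judged possibly or probably related to the vector. Use the same definition wherever DLTs are counted. If the Manual of Procedures already defines the terms, make the two texts agree.

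The cost is one sentence. Grade 3 events that fall below Grade 3 within seven days remain non-DLT, as now. Grade 4 events no longer need a seven-day classification, so the rule requires less timing information than at present. The documents do not state enrolment status. If dosing is complete, the change still governs how DLTs are classified and reported.
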